#### Baseline data

Baseline data from volunteers will be collected during the week prior to vaccination by home visits (Appendix III). The laboratory specimens will be collected prior to vaccination on the day of immunization. The laboratory assays will include blood for immunological assays and stool for culture and routine examination for ova and parasites and immunogical assays. These data will serve as baseline values for the study subjects.

#### Safety evaluation

The primary end point for evaluating safety will be defined as the occurrence of any of the following diarrhoea, vomiting or abdominal cramps of at least moderate grade. Diarrhea will be defined as three or more loose or liquid stools in any 24-h period. A measured oral or rectal temperature above 38°C will be considered a fever.

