#### Safety Monitoring of the Vaccine

On each study day (Days 0,7,14 and 21) clinical history and physical examination will be carried out (Appendix IV). The safety and reactogenicity of the vaccine will be monitored in the subjects by observing for 30 minutes after each dose for occurrence of immediate adverse experiences. On 3 consecutive days after each dose parents will be interviewed for 24 hour recall of symptoms by the health workers and the physician by home visits each day. All side-effects will be recorded in reaction surveillance forms for local and systemic reactions (Appendix V). Reported symptoms will be graded as mild, moderate and severe. In case of serious adverse effects the data will be entered in a separate form (Appendix V). The study subject will be hospitalized at the CRSC of ICDDR,B under supervision of the clinician monitoring the safety of the vaccine. Sample collection

Stool: Stool will be collected prior to vaccination (3 days prior to initial immunization) and subsequently at follow-up visits 7 days after intake of the first as well as 7 days after intake of the second dose of the vaccine. Routine examination of stools will be carried out to detect parasites. Bacteriological examination will be carried out to exclude the presence of enteric pathogens (WHO, 1987). Five lactose-fermenting colonies will be tested for colonization factor expression by dot blot immunoassay techniques and for the enterotoxins LT and ST. Stools will be also be tested prior to intake of the second dose and tested similarly. The stools will also be tested to exclude the presence of ETEC by assaying for LT and ST using the GM1-ELISA technique ([name] and Holmgren, 1978; [name] et al., 1986). Stools will also be collected for preparing faecal extracts for antibody and cytokine assays. Faecal extracts will be prepared (Qadri et al., 1997) and stored at -70°C until tested.

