#### 3.0 SYSTEMIC REACTION

| Parameters   |              |
|--|--------------|
| Fever (oral or rectal temp>37.8°C If yes, temperature (°C) | 1= No 2= Yes |
| Loss of appetite/ Poor feeding                             | 1= No 2= Yes |
| Irritability   | 1= No 2= Yes |
| Nausea   | 1= No 2= Yes |
| Dizziness  | 1= No 2= Yes |
| Exanthema  | 1= No 2= Yes |
| Other  | 1= No 2= Yes |

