1.0 Completeness of dosing. Amount ingested: 1=100%  $2=\ge 90\%$  3=<90%

#### 2.0 LOCAL REACTION

| Parameters  |                                   |
|---|-----------------------------------|
| Abdominal pain  | 1= No 2=Mild 3= moderate 4=severe |
| Cramp   | 1= No 2= Yes                      |
| Distension  | 1=No 2= moderate 3= severe        |
| Vomiting  | 1=No 2= Yes                       |
| If yes, number/day                                      |                                   |
| Other symptoms *Diarrhoea [watery stool or loose stool] | 1=No 2= Yes                       |
| If yes above number/day (> 3)                           |                                   |

\*Diarrhoea defined as passing of ≥ 3 loose or liquid stools per day

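### The adverse-event form records cramp only as yes or no, so the cramp component of the primary safety endpoint cannot be derived as defined

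*Protocol*

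**What the plan says.** The Protocol's Safety evaluation section makes the primary safety endpoint a composite: any of "diarrhoea, vomiting or abdominal cramps of at least moderate grade". It then settles diarrhoea by a count: "Diarrhea will be defined as three or more loose or liquid stools in any 24-h period". The section Safety Monitoring of the Vaccine adds that "Reported symptoms will be graded as mild, moderate and severe", with parents asked daily, on the three days after each dose, about the previous 24 hours.

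The data come from Appendix V, which has six forms, one for each of three days after the primary and the secondary vaccination. Under Local reaction each form has a row "Cramp | 1= No 2= Yes" and a row "Vomiting | 1=No 2= Yes". The vomiting row is followed by "If yes, number/day". A separate row, Abdominal pain, has four levels from none to severe. Diarrhoea has its own definition and a stool number.

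The Data analysis section compares the proportions with the primary outcome between vaccine and placebo after each dose, by the profile likelihood method.

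On fever, Safety evaluation says "A measured oral or rectal temperature above 38°C will be considered a fever", while each form prints "Fever (oral or rectal temp>37.8°C".

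**The concern.** The endpoint needs a severity grade for cramp, the monitoring text promises one, and the form that collects the data has nowhere to write it. Whoever builds the analysis variable would have to count every cramp, count none, or borrow the grade of another symptom. Each choice gives a different endpoint, and the protocol selects none of them. This is the study's only stated primary safety outcome, so the comparison of vaccine with placebo would rest partly on an undocumented choice.

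The fault lies in data capture. The information is a parent's recall of the previous day, and an analysis plan written later cannot supply a grade that nobody asked for.

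**Working it through.** No sample size or power figure is involved, so the check sets the endpoint beside the form, component by component.

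| Component | What the endpoint needs | What each of the six forms collects | Derivable? |
|---|---|---|---|
| Diarrhoea | Three or more loose or liquid stools in 24 hours | Same definition in the footnote, plus a stool number | Yes |
| Vomiting, if the qualifier covers cramps only | Any vomiting | No/yes, plus number per day | Yes |
| Vomiting, if the qualifier covers it too | At least moderate | No/yes, plus number per day; no rule from count to grade | No |
| Abdominal cramps | At least moderate, on either reading | No/yes | No |

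**Step 1: scope of the qualifier.** The sentence in Safety evaluation can be read with the grade attached to cramps alone or to vomiting as well. Cramp is covered on both readings, so the cramp gap does not depend on the reading; the vomiting gap does. I treat diarrhoea as settled by its own count definition, which follows directly.

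**Step 2: who cannot be classified.** Write the endpoint after one dose as D or V or C, where C means cramp of at least moderate grade on any of the three days. A child with D = yes meets the endpoint whatever the cramp entry. The children who cannot be classified are:

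- narrow reading (grade on cramps only): no diarrhoea, no vomiting, cramp ticked at least once;
- wide reading (grade on vomiting too): no diarrhoea, and cramp or vomiting ticked at least once.

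If u is the proportion of such children in an arm and q the proportion who meet the endpoint for certain, the true proportion lies between q (count none) and q + u (count all). The between-arm difference is therefore known only to within the two values of u. The documents give no figure for u.

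**Step 3: other fields.** Abdominal pain is graded but is listed apart from Cramp, so the two rows can disagree: a parent may report cramp with mild pain, or pain with no cramp. Nothing in the protocol links them. The history form in Appendix IV has abdominal distension and tenderness but no cramp item. Extra home visits under Data management can fill blank entries, but a grade with no field on the form is not a blank entry.

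**Step 4: fever.** The thresholds differ by 38.0 − 37.8 = 0.2 °C. Any temperature above 38 °C is also above 37.8 °C, and the form asks for the measured value when the box is ticked. Cases above 38 °C can therefore be recovered from the recorded value, although the yes/no box itself follows the other definition. Fever is not a component of the primary endpoint.

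**The case against.** The strongest reply is that turning form fields into analysis variables is ordinary work for a statistical analysis plan, which is not shown. The codes stay closed until all clinical and laboratory evaluation is complete, so a rule such as cramp ticked together with at least moderate abdominal pain on the same day could be fixed blind from fields already collected. That would be a workable substitute, and it is one of the remedies below. It remains a substitute: it grades a different row, the two rows can disagree, and the protocol defines the endpoint by the grade of the cramp. A later plan can choose the stand-in but cannot produce the endpoint as written.

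Several stronger readings are tempting, and the documents do not support them:

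- A reader might infer that the form cannot deliver the primary endpoint at all. Diarrhoea is fully captured, and vomiting is too if the qualifier is confined to cramps.
- A reader might infer that vomiting is recorded only as yes or no. Every form also asks for the number per day, so a count rule would suffice.
- A reader might take the 2–6% adverse-event rate quoted in the Background as the size of the misclassification. That figure mixes nausea, mild cramps and one or two loose stools a day, and the share due to mild cramp is not given. It occurred in vaccine and placebo recipients alike. Counting mild cramps would add noise, but how much is unknown.
- A reader might cite the two fever thresholds, or the lack of a mild option for distension, as further evidence. Neither symptom is in the primary endpoint.

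**Conclusion.** The inconsistency is real and is the same on all six forms. As written, the cramp component of the primary safety endpoint cannot be derived from its own field, and a child whose only event is a ticked cramp box has no defined outcome. The gap is one component of three for certain, and two if the qualifier extends to vomiting. Its effect on the arm proportions cannot be sized from the documents, and no figure is claimed.

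The conclusion assumes that the Appendix V forms shown are those to be used in the field and that no unwritten convention equates abdominal pain with cramp. It merits correction before first enrolment, because the missing grade cannot be collected afterwards. The fever discrepancy is a separate, minor point.

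**What to change.** Before the first child is enrolled:

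1. On all six Appendix V forms, code Cramp as none, mild, moderate or severe. Alternatively, state in Safety evaluation that the Abdominal pain grade is the source for the cramp component, and say how the two rows combine when they disagree.
2. State in Safety evaluation whether the requirement of at least moderate grade covers vomiting as well as cramps.
3. If it does, add a vomiting grade to the forms, or pre-specify which number per day counts as moderate.
4. Give a short written description of each grade used, so that health workers code alike; the protocol does not describe any of them.
5. As a separate tidy-up, reconcile the fever definition in Safety evaluation with the one printed on the forms.

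The cost is a revised form that is slightly longer to complete at each home visit, and a sentence or two in the protocol. The sample size and the analysis method need no change.

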#### 3.0 SYSTEMIC REACTION

| Parameters               |              |
|--------------------------|--------------|
| Fever (oral or rectal    | 1= No 2= Yes |
| temp>37.8°C              |              |
| If yes, temperature (°C) |              |
| Loss of appetite/ Poor   | 1= No 2= Yes |
| feeding                  |              |
| Irritability             | 1= No 2= Yes |
| Nausea                   | 1= No 2= Yes |
| Dizziness                | 1= No 2= Yes |
| Exanthema                | 1= No 2= Yes |
| Other                    | 1= No 2= Yes |

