#### 3.0 SYSTEMIC REACTION

| Parameters                        |              |
|-----------------------------------|--------------|
| Fever (oral or rectal temp>37.8°C | 1= No 2= Yes |
| If yes, temperature (°C)          |              |
| Loss of appetite/ Poor            | 1= No 2= Yes |
| feeding                           |              |
| Irritability                      | 1= No 2= Yes |
| Nausea                            | 1= No 2= Yes |
| Dizziness                         | 1= No 2= Yes |
| Exanthema                         | 1= No 2= Yes |
| Other                             | 1= No 2= Yes |

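### Fever is defined by a measured temperature, but it is collected by daily parental recall on a form that does not separate measured, reported and unmeasured fever, so fever may be undercounted

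*Protocol*

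**What the plan says.** **Definition.** Protocol, Safety evaluation: "A measured oral or rectal temperature above 38°C will be considered a fever".

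**Primary safety endpoint.** The same section says: "The primary end point for evaluating safety will be defined as the occurrence of any of the following diarrhoea, vomiting or abdominal cramps". Fever is not a component.

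**Collection.** Protocol, Safety Monitoring of the Vaccine: "On 3 consecutive days after each dose parents will be interviewed for 24 hour recall of symptoms by the health workers and the physician", at a home visit each day. The other contacts in that section are "observing for 30 minutes after each dose for occurrence of immediate adverse experiences" and "On each study day (Days 0,7,14 and 21) clinical history and physical examination will be carried out".

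**Form.** Each of the six daily sheets in Appendix V has one fever line under 3.0 Systemic Reaction, "Fever (oral or rectal temp>37.8°C", answered No or Yes, followed by "If yes, temperature (°C". The sheets have no space for the time of the reading, its route or who took it, and no code for a fever that was reported but not measured.

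**Analysis.** Protocol, Data analysis: individual symptoms are compared between arms with Fisher's exact test, two-tailed. The two age groups are analysed together and separately.

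**The concern.** The definition and the data source do not fit together. An interview can establish loose stools in the past day. It cannot produce a thermometer reading for last night unless somebody took one, and the protocol does not arrange for that. When a parent says the child was hot overnight and no reading exists, the definition makes it not a fever, while the 24-hour recall and the form invite a 'Yes'. No rule decides between them.

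The form adds a second gap. Because a temperature is written down only after a 'Yes', an afebrile child with a reading and a child whose temperature was never taken both appear as 'No'.

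What is at stake is the sensitivity of one safety comparison. Safety is the first specific aim, and a weak comparison of a safety symptom errs towards false reassurance. A temperature that was never taken, or a measured/reported distinction that was never recorded, cannot be restored later by any analysis plan.

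**Working it through.** **1. Where a qualifying temperature could come from in the three days after a dose.** Doses are two weeks apart, so with dosing on Days 0 and 14 the home-visit windows are Days 1–3 and 15–17.

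| Contact | When | Covers fever on Days 1–3 or 15–17? |
|---|---|---|
| Direct observation | 30 minutes after each dose | No |
| Scheduled examination (Appendix IV, has a temperature field) | Days 0, 7, 14, 21 | No; none of these days falls in a window |
| Home visit with recall (Appendix V) | Once a day, 3 days after each dose | Yes, but no instruction says that the visitor takes a temperature |
| Readings by parents between visits | Not mentioned | Neither provided for nor excluded |

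The 5% re-interview and the extra visits to complete forms (Methods to ensure data quality; Data management) cannot supply a reading that was never taken.

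**2. Effect on the comparison.** The protocol gives no fever rate and no capture fraction, so there is no figure of its own to reproduce. Let c and v be the true fever risks on placebo and vaccine, and s the fraction captured, equal in both arms because the surveillance is the same and blinded.

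- Observed risks: s·c and s·v.
- Risk ratio: (s·v)/(s·c) = v/c, unchanged.
- Risk difference: s·(v − c), reduced by the factor s.
- If v = c, the observed risks stay equal, so no false difference is created.

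**3. What s might be.** If, as a worst case, a fever counts only when present at a single daily visit, a fever of D hours (D < 24) is caught with probability D/24: 12/24 = 50% for 12 hours and 6/24 = 25% for 6 hours. These durations are assumptions.

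**4. Illustration of the power loss.** Sample size calculation gives 158 children in each age group, or 2 × 158 = 316 in all. Assuming 1:1 allocation and no losses, that is 158 per arm pooled and 79 per arm within one age group. The test is Fisher's exact test, two-sided 5%, with power summed over the two binomial distributions. The rates are assumed.

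| Assumed true risks | Per arm | s = 1 | s = 0.5 | s = 0.25 |
|---|---|---|---|---|
| 5% v 20% | 158 | 98.2% | 74.6% | 35.3% |
| 5% v 20% | 79 | 78.7% | 36.5% | 9.3% |
| 5% v 15% | 158 | 81.8% | 43.3% | 16.5% |

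For 5% v 20%, the observed risks are 2.5% v 10% at s = 0.5 and 1.25% v 5% at s = 0.25. The direction does not depend on the rates chosen; the amount does.

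**The case against.** A reader might infer that fevers settling between visits cannot be scored at all. The documents do not say so. The definition does not confine measurement to the visit, the recall window covers the time between visits, and the form does not say when its temperature was taken. The form also offers 'resolved' as an outcome, so it expects events that are over by the time of the visit. A reading taken at home and reported would qualify. What stands is narrower: no such reading is provided for, and a fever without one has no coding rule.

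A reader might also infer that the fever comparison is biased or loses most of its power. Bias between arms is not supported, because allocation is randomized and blinded and surveillance is the same in both. The power loss depends wholly on assumed rates and durations; with 158 per arm and half of fevers captured, the first illustration keeps 75%.

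The importance of fever should not be inflated either. It lies outside the primary safety endpoint, and nothing in the sample size calculation refers to it. The Background's account of earlier studies lists nausea, mild abdominal cramps and loose stools in about 2–6% of recipients and does not mention fever. Nothing in the protocol makes fever the main systemic reaction at this age.

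Finally, requiring a measured temperature is a sound, objective definition, and counting parent-felt fever in the main outcome would give up specificity. That objection stands and shapes the fix.

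**Conclusion.** The mismatch is real and worth correcting before data collection, as a modest improvement. The protocol counts only a measured temperature, gathers symptoms by daily recall without arranging readings, and uses a form on which a reported but unmeasured fever has no place and 'No' does not mean 'measured and normal'. Fever may therefore be undercounted or coded inconsistently.

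The consequence is limited to a secondary symptom comparison. Absolute fever rates and the power to detect an excess may fall; the ratio between arms, the type I error, the primary safety endpoint and the sample size are not affected. This rests on capture being equal in the two blinded arms. The documents do not give the size of the loss, and the power figures above only show what different capture fractions would do.

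Separately, the fever cut-off is above 38°C under Safety evaluation and above 37.8°C in Appendix V. A child at 37.9°C is a 'Yes' on the form and not a fever by the text. The two must be reconciled, but doing so would not settle the measured-versus-recalled problem.

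**What to change.** Split the fever item on each Appendix V sheet into two:

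1. Temperature measured at this visit, with value and route, recorded for every child whatever the answer on fever.
2. Fever felt or measured by the parent since the last visit, yes or no, with the value if one was measured.

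Keep measured fever as the main fever outcome. Report measured or parent-reported fever by arm as a sensitivity analysis.

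The cost is two form lines, one extra analysis line and a thermometer reading at visits already planned. The drawback is that parent-felt fever is less specific, and false positives would also dilute a true difference, which is why it belongs in the sensitivity analysis. Reconcile the two temperature cut-offs in the same revision.

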#### Vaccine and placebo composition, allocation and administration

The ETEC BSA-CF ETEC vaccine is produced by SBL Vaccin AB (Stockholm, Sweden) One 4 ml dose contains 1.0 mg recombinantly produced CTB plus 2x10^10 formalin inactivated bacteria of each of the following ETEC strains: SBL101 (O78:H12; CFA/I; ST+); SBL104 (O25:H42; CS4+CS6); SBL 105 (O167:H5; CS5+ CS6; ST+); SBL106 (06:H16; CS1); and SBL107 (OR:H6;CS2+CS3). SBL101 and SBL105 are washed prior to formulation to remove any heat stable enterotoxin (ST) activity. The placebo dose will consist of 1x10^11 heat-killed *E. coli* K-12 bacteria (SBL vaccin).

Healthy boys and girl will be recruited in the study from the urban suburbs around Dhaka city. Children will be excluded from enrollment if interviewers find a history of chronic gastrointestinal disorder, diarrhoea in the past two weeks, febrile illness in the preceding week or some other serious chronic illness. Subjects will be given two doses of the study agent 2 weeks apart and will not be allowed to eat or drink for about 60 min before and after each dose. They will however be allowed to drink water during this period if necessary. Previous experience with the ETEC vaccine in Egypt has shown that in children 6-18 months of age this was suitable.

Immediately before use individual doses of the vaccine will be mixed with the reconstituted bicarbonate buffer. For children 18 months -3 years of age, the vaccine (4 ml) will be dissolved in 30 ml (total 7 teaspoon) of a raspberry flavored bicarbonate buffer [the buffer is prepared by adding 100 ml water to a sachet of bicarbonate buffer; Recip AB, Stockholm of which 30 ml will be used to prepare the vaccine dose]. For younger children the vaccine will be administered in 15 ml of the buffer (about 4 teaspoon) [prepared by adding 75 ml water to a sachet of the above buffer of which 15 ml will be used] and given to the child. This is the procedure followed for immunization of children in the different age groups in Egypt and has been found suitable since in most cases the total dose of the vaccine was ingested. Informed consent will be taken from the parent/guardian of the children for the safety studies or for the safety and for permission to draw blood (Appendices Ia, Ib, IIa, IIb).

Study subjects taking at least 90% of the vaccine dose will be kept enrolled in the study but the data will be analyzed separately as well as with the others to see differences in the immune response.

| Principal 1 | nvestigator: | Last, first. | middle | 1 |  |  |  |
|-------------|--------------|--------------|--------|---|--|--|--|
|             |              |              |        |   |  |  |  |

